9.4.2.2. Treatment Period

9.4.2.2.1. Visit 2 (Day 1) - Predose

Subjects will continue to be confined at the clinic during Visit 2 (Day 1) and will undergo the following assessments before administration of study drug:

- [REDACTED]
 - █ [REDACTED]
 - █ [REDACTED]
- Vital signs
- Standard 12-lead ECG
- Body weight
- Laboratory assessments:
 - Chemistry and hematology
 - Urinalysis (MAD-HS and MAD-CP only)
- █ [REDACTED]
- █ [REDACTED]
- █ [REDACTED]
- █ [REDACTED]
- Assessment of concomitant medication usage
- Assessment of AEs
- Blood sample draw for PK assessment

- [REDACTED]
- Randomization to EP547 or placebo in a 3:1 ratio

Upon completion of the assessments listed above, study drug is to be administered orally as intact capsules (swallowed whole, not chewed or crushed), and taken with water.

9.4.2.2.2. Visit 2 (Day 1) - Postdose

Subjects will continue to be confined at the clinic during Visit 2 (Day 1) and will undergo the following assessments before administration of study drug:

- Assessment of concomitant medication usage
- Assessment of AEs
- [REDACTED]
- Blood sample draw for PK assessment at 0.25, 0.5, 1, 1.5, 2, 2.5, 3, 4, 6, 9, and 12 hours postdose
- Vital signs at 1, 2, 4, 9, and 12 hours postdose
- Skin biopsies for PK [REDACTED] at 2 hours postdose (last dose level for MAD-HS and all dose levels for MAD-CP and MAD-UP only)
- Laboratory assessment:
 - [REDACTED]
- Standard 12-lead ECG at 3 hours postdose
- Hemodialysis 4 to 6 hours postdose (MAD-UP only)

9.4.2.2.3. Visit 2 (Day 2)

Subjects will continue to be confined at the clinic during Visit 2 (Day 2) and will undergo the following assessments:

- Vital signs
- Laboratory assessments:
 - Chemistry and hematology
 - Urinalysis (MAD-HS and MAD-CP only)
 - [REDACTED]
- Assessment of concomitant medication usage
- Assessment of AEs
- [REDACTED]

- Blood sample draw for PK assessment:
 - At 18 hours postdose relative to the dose of study drug on Day 1
 - Predose (all MAD segments) and at 0.25, 0.5, 1, 1.5, 2, 2.5, 3, 4, 6, 9, and 12 hours postdose relative to the dose of study drug on Day 2 (MAD-UP only)
- Administer study drug orally as intact capsules (swallowed whole, not chewed or crushed) with water at approximately the same time of day as the dose administered on Day 1

Subjects in MAD-CP and MAD-UP may be discharged from the clinic after completion of all of the assessments listed above if they choose to return to the site each morning or have a nurse visit their home until the next mandatory confinement period (Day 6 to Day 8 for MAD-UP and Day 7 to Day 8 for MAD-CP) to complete scheduled assessments. Subjects in MAD-HS must remain confined to the study site through Day 8.

9.4.2.2.4. Visit 2 (Day 3)

Subjects in MAD-HS will continue to be confined at the clinic during Visit 2 (Day 3). Subjects in MAD-CP and MAD-UP may choose to remain confined, return to the site, or have a nurse visit their home for Visit 2 (Day 3). Subjects will undergo the following assessments for Visit 2 (Day 3):

- Vital signs
- Standard 12-lead ECG
- Assessment of concomitant medication usage
- Assessment of AEs
- [REDACTED]
- Blood sample draw for PK assessment:
 - At 18 hours postdose relative to the dose of study drug on Day 2 (MAD-UP only)
 - Predose relative to the dose of study drug on Day 3 (MAD-HS only)
- Administer study drug orally as intact capsules (swallowed whole, not chewed or crushed) with water at approximately the same time of day as the dose administered on Day 1
- [REDACTED]

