7.1.4.2. Multiple Dose Segments

Screening: Visit 1 (Screening) is to occur between Day -28 and Day -4.

Blinded Treatment Period: There is 1 confinement period in the clinic (Visit 2), beginning from Day -1 (admission) to Day 8 until after the 24-hour post-last dose assessments are completed (discharge). The full confinement period is mandatory for MAD-HS. For Day 3 through Day 6 in MAD-CP and Day 3 through Day 5 in MAD-UP, subjects may choose to remain confined, return to the site each morning, or have a nurse visit their home to complete scheduled assessments.

Safety Follow-Up: Visit 3 (Follow-Up Visit 1) and Visit 4 (Follow-Up Visit 2) are to occur approximately 1 and 2 weeks after the last dose of study drug, respectively. Subjects are to return to the site to complete scheduled assessments for Safety Follow-Up Visits. However, a nurse visit to their home may be permitted on a case-by-case basis with prior approval of the Sponsor.

Figure 3: Study Schedule for the Multiple-Dose Segments

CP = cholestatic pruritus; HS = healthy subject; MAD = multiple ascending dose; PO = oral; QD = once daily; UP = uremic pruritus

Shading represents the period when subjects may be confined to the study site.

^a Subjects are to return to the site to complete scheduled assessments for Safety Follow-Up Visits. However, a nurse visit to their home may be permitted on a case-by-case basis with prior approval of the Sponsor.

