For PK parameter data, the number of non-missing values, arithmetic mean, standard deviation, geometric mean, geometric SD, geometric CV, median, minimum and maximum values will be presented. Individual PK parameters will be presented to three significant figures with the exception of  $T_{max}$  which will be presented to two decimal places.

- Categorical variables: Descriptive statistics will include counts and percentages per category. The denominator in all percentage calculations will be the number of participants in the relevant analysis population with non-missing data, unless specifically stated otherwise. Percentages will be displayed to one decimal place. Proportions will be displayed to 3 decimal places.
- Repeat/unscheduled assessments: Only values collected at scheduled study visits/time points will be presented in summary tables. If a repeat assessment was performed, the result from the original assessment will be presented as the result at the specific visit/time point. All collected data will be included in the data listings.

- Assessment windows: All assessments will be included in the data listings and no visit windows will be applied to exclude assessments that were performed outside of the protocol specified procedure windows.
- Result display convention: Results will be center aligned in all summary tables and listings. Participant identifiers visit and parameter labels may be left-aligned if required.
- Date and time display conventions: The following display conventions will be applied in all outputs where dates and/or times are displayed:

Date only: YYYY-MM-DD

Date and time: YYYY-MM-DD HH:MM

If only partial information is available, unknown components of the date or time will be presented as 'NK' (not known), i.e., '2016-NK-NK'. Times will be reported in military time.

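### In MAD-UP the 18 h sample that ends the Day 2 profile falls after permitted discharge and about 6 h before the Day 3 dose, with no visit set to collect it and no predose sample as backup

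*Protocol*

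**What the plan says.** - **Day 2 (Protocol 9.4.2.2.3).** The MAD-UP samples listed for Day 2 end at "12 hours postdose relative to the dose of study drug on Day 2 (MAD-UP only"). The text below that list reads: "Subjects in MAD-CP and MAD-UP may be discharged from the clinic after completion of all of the assessments listed above". This applies to those who opt for daily site attendance or home nursing. Their next compulsory stay is given as "Day 6 to Day 8 for MAD-UP and Day 7 to Day 8 for MAD-CP".
- **Optional days (Protocol 7.1.4.2).** For Days 3 to 5 of this segment the rule is: "subjects may choose to remain confined, return to the site each morning, or have a nurse visit their home to complete scheduled assessments".
- **Day 3 (Protocol 9.4.2.2.4).** The options given are that they "may choose to remain confined, return to the site, or have a nurse visit their home for Visit 2 (Day 3"). The Day 3 list includes a blood draw "At 18 hours postdose relative to the dose of study drug on Day 2 (MAD-UP only"). Appendix C gives it a ±15 minute window. The Day 3 predose PK sample is for MAD-HS only. The Day 3 dose is due at about the same clock time as the Day 1 dose, and the Day 3 vital signs and ECG are predose (Protocol 11.5 and 11.8).
- **Analysis.** SAP 10.1 derives MAD-UP plasma parameters for Days 1, 2, 6 and 7. Protocol 15.5 and SAP 10.1 use actual sampling times for these. Concentrations are summarised by nominal time, and under SAP 3.1 "no visit windows will be applied to exclude assessments that were performed outside of the protocol specified procedure windows". SAP 3.5 lets the pharmacokineticist leave a badly mistimed concentration out of the descriptive summaries.

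**The concern.** The discharge rule and the sampling schedule do not fit together. A site that follows 9.4.2.2.3 to the letter may release a subject who is then due for a draw in the night. The next contact the protocol describes is a morning or home visit at which the Day 3 dose is given. The Day 2 profile of that subject then either stops at 12 h or carries a last sample taken hours off schedule. Day 2 is the first MAD-UP profile without a dialysis session (sessions are on Days 1, 4 and 6), and the SAP reports parameters for it.

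**Working it through.** No figure in the plan bears on this, so the check is clock arithmetic followed by an illustration of size.

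**1. Timing.** Take the Day 2 dose as time 0 and the dosing interval as 24 h.
- Last sample required before discharge: 12 h. Sample in question: 18 h. Day 3 dose: about 24 h.
- Gap after permitted discharge: 18 − 12 = 6 h. Gap before the Day 3 dose: 24 − 18 = 6 h.
- The 12 h sample is listed on Day 2 and the 18 h sample on Day 3, so the dose lies between about 06:00 and 12:00. The 18 h draw is then due between about 00:00 and 06:00 (an 08:00 dose gives 02:00).
- If the draw is made in the last 30 minutes before the Day 3 dose, it is at 23.5 to 24 h. That is 330 to 360 minutes late, and 330/15 = 22 to 360/15 = 24 times the window.

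**2. Is this the only exposed 18 h sample?** From 9.4.2.2 and Appendices B and C:

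| MAD-UP dose | 18 h sample falls on | Confinement that day | Next PK sample before the following dose |
|---|---|---|---|
| Day 1 | Day 2 | mandatory | Day 2 predose |
| Day 2 | Day 3 | optional | none |
| Day 6 | Day 7 | mandatory | Day 7 predose |

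The Day 7 profile has no 18 h sample but has one at 24 h, on Day 8, in confinement. So the Day 2 profile is the only one exposed, and it has no backup.

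**3. If the sample is missed.** The only half-life in the protocol is the monkey value of about 18 h (5.3), so a range of 6 to 48 h is assumed. With mono-exponential decline, k = ln 2 / half-life, and the share of AUC0-24 after the last sample at time s is (e^(−ks) − e^(−24k)) / (1 − e^(−24k)). At 18 h:
- s = 12: (0.630 − 0.397) / (1 − 0.397) = 0.386
- s = 18: (0.500 − 0.397) / (1 − 0.397) = 0.171

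A fuller illustration uses a one-compartment oral model with tmax 2 h, two daily doses and no dialysis clearance. The AUC is by linear-up/log-down at the scheduled times:

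| Assumed half-life | Beyond last sample, 18 h taken | Beyond last sample, 18 h missed | AUC%extrap, taken / missed |
|---|---|---|---|
| 6 h | 7.5% | 22.1% | 14% / 27% |
| 12 h | 14.4% | 34.7% | 36% / 51% |
| 18 h | 17.6% | 39.6% | 51% / 64% |
| 24 h | 19.3% | 42.3% | 60% / 71% |
| 48 h | 22.2% | 46.3% | 77% / 84% |

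SAP 10.1.1.2 sets regression-based parameters to not calculable unless AUC%extrap is below 20%. In this model they are lost either way at half-lives of 12 h or more. Only at 6 h does the missing sample itself cross the limit (14% to 27%).

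**4. If the sample is drawn 6 h late.** Filed under nominal 18 h, the value reads 2^(−6/half-life) of the true 18 h value. At 18 h that is 0.794, about 21% low. At 6 h it is 0.50 (50% low) and at 48 h it is 0.917 (8% low). In the parameter calculation the same value enters at about 24 h.

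**5. Numbers exposed.** Each level has 8 to 12 subjects at 3:1, so 6 to 9 on EP547. How many would leave on Day 2 is not stated.

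**The case against.** Four objections have weight.

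- **Loss is not certain.** The 18 h sample stays required after discharge, subjects may choose to stay in, and no clock time or single-contact limit is set for the nurse visit. A reader might infer that every outpatient subject loses or mistimes the sample; the text does not go that far. What stands is that the site option is each morning and that the protocol provides for no night visit.
- **A late draw does not bias AUC.** Actual times are used, so a draw just before the Day 3 dose covers nearly the whole interval, better than a punctual 18 h sample would. This stands in full. The damage is then one nominal-time row, which SAP 3.5 allows to be cleaned.
- **No dialysis contrast depends on Day 2.** It is tempting to treat Day 2 as the comparator for the Day 1 dialysis interval. Neither document plans that comparison, and it would mix dialysis with first-dose versus second-dose accumulation. Days 6 (dialysis) and 7 (no dialysis) give a full pair inside mandatory confinement, each followed to about 24 h. The SAP's inferential PK is limited to dose proportionality in SAD-HS and MAD-HS and to the food effect.
- **The percentages are illustrative.** They rest on an animal half-life and a simple model, and an unobserved share is not the same as bias. That is why the range is shown.

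**Conclusion.** The conflict is in the text and rests on no assumption beyond a 24 h dosing interval: discharge is allowed at 12 h, a sample is due at 18 h ±15 minutes, and the next visit provided for is at about 24 h. For subjects who leave on Day 2, a missed or late sample is likely. If it is missed, the unobserved part of the Day 2 AUC0-24 roughly doubles at an assumed 18 h half-life, from about 18% to 40% (8% to 22% at 6 h; 22% to 46% at 48 h). If it is late but taken before the Day 3 dose, the harm is confined to the nominal 18 h summary, unless the value is excluded. The scope is one sample per outpatient subject in a descriptive secondary analysis. It should be corrected because the plan cannot be followed as written at a single morning visit, but it threatens no planned comparison.

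**What to change.** Reconcile the synopsis (Study Schedule), 7.1.4.2 with Figure 3, 9.4.2.2.3, 9.4.2.2.4, the MAD-UP confinement and discharge rows and note in Appendix B, and Appendix C. Either of two changes does it:

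1. **Later discharge.** Set the earliest MAD-UP discharge after the 18 h sample of the Day 2 dose. The cost is one more clinic night for those who would have left; no samples or visits are added.
2. **Different sample for leavers.** For subjects discharged on Day 2, replace the 18 h draw with a Day 3 predose PK sample at the visit already scheduled, and also amend 12.1 and the matching synopsis text on blood sampling. This adds no clinic night and no draw, and it closes the Day 2 dosing interval. The cost is that the last nominal time of the Day 2 profile then differs between subjects who stay and subjects who leave, so the concentration table needs a separate row for the predose sample.

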9.4.2.2.5. Visit 2 (Day 4)

Subjects in MAD-HS will continue to be confined at the clinic during Visit 2 (Day 4). Subjects in MAD-CP and MAD-UP may choose to remain confined, return to the site, or have a nurse visit their home for Visit 2 (Day 4). Subjects will undergo the following assessments for Visit 2 (Day 4):

- [REDACTED]
- Vital signs
- Laboratory assessments:
 - Chemistry and hematology
 - Urinalysis (MAD-HS and MAD-CP only)
- Assessment of concomitant medication usage
- Assessment of AEs
- [REDACTED]
- Blood sample draw for PK assessment predose relative to the dose of study drug on Day 4
- Administer study drug orally as intact capsules (swallowed whole, not chewed or crushed) with water at approximately the same time of day as the dose administered on Day 1
- Hemodialysis 4 to 6 hours postdose (MAD-UP only)

9.4.2.2.6. Visit 2 (Day 5)

Subjects in MAD-HS will continue to be confined at the clinic during Visit 2 (Day 5). Subjects in MAD-CP and MAD-UP may choose to remain confined, return to the site, or have a nurse visit their home for Visit 2 (Day 5). Subjects will undergo the following assessments for Visit 2 (Day 5):

- [REDACTED]
- Vital signs
- Assessment of concomitant medication usage
- Assessment of AEs
- [REDACTED]
- Blood sample draw for PK assessment predose relative to the dose of study drug on Day 5 (MAD-HS only)
- Administer study drug orally as intact capsules (swallowed whole, not chewed or crushed) with water at approximately the same time of day as the dose administered on Day 1

9.4.2.2.7. Visit 2 (Day 6)

Subjects in MAD-UP will be admitted for confinement at the clinic and subjects in MAD-HS will continue to be confined at the clinic during Visit 2 (Day 6). Subjects in MAD-CP may choose to remain confined, return to the site, or have a nurse visit their home for Visit 2 (Day 6). Subjects will undergo the following assessments for Visit 2 (Day 6):

- [REDACTED]
- Vital signs
- Assessment of concomitant medication usage
- Assessment of AEs
- [REDACTED]
- Blood sample draw for PK assessment:
 - Predose relative to the dose of study drug on Day 6 (MAD-HS and MAD-UP only)
 - At 0.25, 0.5, 1, 1.5, 2, 2.5, 3, 4, 6, 9, and 12 hours postdose relative to the dose of study drug on Day 6 (MAP-UP only)
- Administer study drug orally as intact capsules (swallowed whole, not chewed or crushed) with water at approximately the same time of day as the dose administered on Day 1
- Hemodialysis 4 to 6 hours postdose (MAD-UP only)

9.4.2.2.8. Visit 2 (Day 7)

Subjects in MAD-CP will be admitted for confinement at the clinic and subjects in MAD-HS and MAD-UP will continue to be confined at the clinic during Visit 2 (Day 7). Subjects will undergo the following assessments for Visit 2 (Day 7):

- [REDACTED]
- Vital signs
- [REDACTED]
- [REDACTED]
- [REDACTED]
- Assessment of concomitant medication usage
- Assessment of AEs
- [REDACTED]

- Blood sample draw for PK assessment:
 - At 18 hours postdose relative to the dose of study drug on Day 6 (MAD-UP only)
 - Predose and at 0.25, 0.5, 1, 1.5, 2, 2.5, 3, 4, 6, 9, and 12 hours postdose relative to the dose of study drug on Day 7
- Administer study drug orally as intact capsules (swallowed whole, not chewed or crushed) with water at approximately the same time of day as the dose administered on Day 1
- [REDACTED]

9.4.2.2.9. Visit 2 (Day 8) - Discharge

Subjects will continue to be confined at the clinic during Visit 2 (Day 8) until completion of the following assessments:

- [REDACTED]
- [REDACTED]
- [REDACTED]
- [REDACTED]
- Laboratory assessment:
 - Chemistry and hematology
 - Urinalysis (MAD-HS and MAD-CP only)
 - [REDACTED]
- Assessment of concomitant medication usage
- Assessment of AEs
- Vital signs at 24 hours postdose relative to the dose of study drug on Day 7
- Standard 12-lead ECG at 24 hours postdose relative to the dose of study drug on Day 7
- Body weight
- Blood sample draw for PK assessment:
 - At 24 hours postdose relative to the dose of study drug on Day 7

Subjects may be discharged from the clinic after completion of all assessments listed above.

9.4.2.3. Safety Follow-Up Period

9.4.2.3.1. Visit 3 (Day 14)

Subjects are to return to the site to complete scheduled assessments for Visit 3 (Day 14). However, a nurse visit to their home may be permitted on a case-by-case basis with prior

approval of the Sponsor. Subjects will undergo the following assessments after an overnight fast (at least 8 hours) during the ± 1 -day visit window for Visit 3 (Day 14):

- [REDACTED]
 - [REDACTED]
 - [REDACTED]
- Abbreviated physical examination
- Vital signs
- Laboratory assessments:
 - Chemistry and hematology
 - Urinalysis (MAD-HS and MAD-CP only)
 - [REDACTED]
 - Serum pregnancy test (females only)
- Assessment of concomitant medication usage
- Assessment of AEs
- Blood sample draw for PK assessment

9.4.2.3.2. Visit 4 (Day 21)

Subjects are to return to the site to complete scheduled assessments for Visit 4 (Day 21). However, a nurse visit to their home may be permitted on a case-by-case basis with prior approval of the Sponsor. Subjects will undergo the following assessments after an overnight fast (at least 8 hours) during the ± 2 -day visit window for Visit 4 (Day 21):

- [REDACTED]
 - [REDACTED]
 - [REDACTED]
- Complete physical examination
- Vital signs
- Laboratory assessments:
 - Chemistry and hematology
 - Urinalysis (MAD-HS and MAD-CP only)
 - [REDACTED]
 - Serum pregnancy test (females only)
- Assessment of concomitant medication usage
- Assessment of AEs

- Blood sample draw for PK assessment

9.4.2.4. Early Study Termination Visit

Subjects who discontinue from the study early should have the Early Study Termination Visit conducted as soon as possible after the last dose of study drug, ideally within 2 days after the last dose of study drug. Subjects are to arrive at the clinic after an overnight fast (at least 8 hours) and will undergo the following assessments during the Early Study Termination Visit:

- [REDACTED]
- [REDACTED]
- [REDACTED]
- Complete physical examination
- Vital signs
- Standard 12-lead ECG
- Body weight
- Laboratory assessments:
 - Serum pregnancy test (females only)
 - Chemistry and hematology
 - Urinalysis (MAD-HS and MAD-CP only)
- Assessment of concomitant medication usage
- Assessment of AEs

10. STUDY DRUG MATERIALS AND MANAGEMENT

10.1. Study Drugs

EP547 lockable capsules will be prepared by the central vendor to contain the desired amount of drug substance to meet the needs of the given dose level. Each lockable placebo capsule will contain placebo such as microcrystalline cellulose and will be manufactured in a way to ensure the study blind. Each dose may be made up of multiple capsules of the same or different capsule strengths.

10.2. Study Drug Packaging and Labeling

Just-in-time manufacturing will be used to supply the study drug, EP547 or placebo capsules, at the specified dose level selected for each segment. Each study drug kit will be labeled with a unique kit number and will be supplied to study sites in a blinded manner. Study drug shipments will be sent to sites with code break envelope(s) containing the treatment assignment(s) that can be utilized by the site for emergency unblinding.

10.3. Study Drug Storage

The study drug capsules may be stored at controlled room temperature, 20°C to 25°C (68°F to 77°F), with excursions to 10°C (50°F).

10.4. Study Drug Administration

Study drug is to be administered orally as intact capsules (swallowed whole, not chewed or crushed), and taken with water. During the MAD segments, doses are to be administered daily at approximately the same time of day over 7 days. There are no fasting or fed requirements for study drug administration (only for study procedures as described in Section 9.4). Subjects who routinely take a bile acid sequestrant (eg, cholestyramine, colestipol, or colesevelam) will be instructed to hold their morning dose until 2 hours after study drug administration. If their bile acid sequestrant baseline dosing regimen does not allow for a 2-hour hold, dosing of these medications must be held for a minimum of 1 hour after study drug administration. Alternatively, the bile acid sequestrant may be taken at least 4 hours prior to study drug administration.

10.5. Additional Dosing Instructions for Subjects with Uremic Pruritus

For subjects in SD-UP, Day 1 (study drug administration) must be the day after a hemodialysis session.

For subjects in MAD-UP, study drug will be administered 4 to 6 hours before the hemodialysis session on Days 1, 4, and 6 and at approximately the same time of day on Days 2, 3, 5, and 7 (days without a hemodialysis session).

10.6. Study Drug Dispensing and Accountability

All study drug is to be administered at the study site. The site staff will be responsible for documenting and maintaining study drug dispensation and accountability records.

